4.2.1.5. Progression-Free Survival

Progression-free survival (PFS) is defined as the time from randomization to disease progression, relapse from CR, CRh, or CRi, or death from any cause, whichever occurs first. Participants who did not reach any of these events will be censored at the last disease assessment.

Number and percent of participants reaching PFS events (overall, disease progression, relapse, or death) will be provided. Kaplan-Meier estimates of the survival functions will be presented graphically. Median and 25th and 75th percentiles along with associated 95% CI will be provided. Analyses will be performed for ITT and MITT populations.

4.2.1.6. Overall Survival

Overall survival (in months) is defined as the time from randomization to death from any cause. For participants who are not known to have died, survival time will be censored at the date last known to be alive.

Number and percent of deaths will be provided. Kaplan-Meier estimates of the survival functions will be presented graphically. Median and 25th and 75th percentiles along with associated 95% CI will be provided. Analyses will be performed for ITT and MITT populations.

5. SAFETY

All safety analyses will be based on the safety analysis set based on actual treatment received, unless otherwise specified. Selected safety parameters may also be summarized separately for participants who have cusatuzumab dose crossover if number of such participants permits.

For all continuous safety variables, descriptive statistics will include the N, mean, standard deviation, median, minimum, and maximum. Categorical variables will be summarized using frequency counts and percentages.

Safety assessment will be evaluated through AEs, clinical hematology and chemistry laboratory tests, death, vital signs, electrocardiogram (ECG) and ECOG performance scores. Safety analyses will be based on the safety analysis set and presented by the actual treatment group.

5.1. Adverse Events

The verbatim terms used in the eCRF by investigators to identify adverse events will be coded using the Medical Dictionary for Regulatory Activities (MedDRA). Toxicities will be graded for severity according to NCI-CTCAE, version 5.0. Intervention-emergent adverse events are adverse events with onset during the intervention phase or that are a consequence of a pre-existing condition that has worsened since baseline. All reported adverse events will be included in the analysis. For each adverse event, the percentage of participants who experience at least 1 occurrence of the given event will be summarized by intervention group. In addition, comparisons between intervention groups will be provided if appropriate.

Specifically, the following will be summarized:

- All adverse events
- Grade 3 or higher adverse events
- Serious adverse events
- Adverse events leading to discontinuation of treatment
- Adverse events leading to death
- Adverse events of special interest

Summaries, listings, datasets, or participant narratives may be provided, as appropriate, for those participants who die, who discontinue intervention due to an adverse event, or who experience a severe or a serious adverse event.

Parameters with predefined National Cancer Institute Common Terminology Criteria for Adverse Events (NCI-CTCAE) toxicity grades will be summarized. Change from baseline to the worst adverse event grade experienced by the participant during the study will be provided as shift tables.

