1.3. Schedule of Activities (SoA)

Table 1: Schedule of Activities Up to 22 Oct 2021

NOTE: As of Amendment 3: After 22 Oct 2021, subjects will no longer follow this SoA. Subjects will be treated and assessed according to Table 1A.

	Screening	Randomization	Treatment		Follow-up
Study Procedure	Within 28 days of randomization	Within 72 hours of first dose	Azacitidine/ cusatuzumab combination therapy (28-day cycle)	EOT ^a	30 days (±3 days) after last dose of study treatment and then every 3 months thereafter (±7 days) ^b
			Cycle 1 – EOT		
Screening/ Administrative					
Informed consent ^c	X				
Demographics/ medical history	X				
Cytogenetic testing/ Mutational analysis	X ^d				
Inclusion/exclusion criteria ^e	X	X			
Study Intervention Administration					
Randomization		X			
Pre-medications ^f			X		
Azacitidine 75 mg/m ² SC or IV ^e			Day 1 to Day 7 of each 28-day cycle		
Cusatuzumab IV infusion at selected dose ^f			Day 3 and Day 17 of each 28-day cycle (+2 days)		
Efficacy Assessments					
Disease evaluation ^g	X ^h		Every other cycle, starting at Cycle 1, (between Day 21 up to and including Day 1 of the next cycle) until CR or progressive disease. Once CR is achieved, disease evaluation can be performed every 4th cycle until relapse. Once CR without MRD is achieved, a repeat bone marrow examination to confirm should be performed at least 4 weeks later. In cases of cycle delays, timing of disease evaluations should be performed per protocol at the end of the specified odd cycle.	X	
Bone marrow aspirate ⁱ	Within 7 days of Cycle 1/ Day 1		At every disease evaluation	X	
Evaluation of extramedullary disease ^j	X		At every disease evaluation as needed	X	
Transfusion status	X		At every disease evaluation	X	

	Screening	Randomization	Treatment		Follow-up
Study Procedure	Within 28 days of randomization	Within 72 hours of first dose	Azacitidine/ cusatuzumab combination therapy (28-day cycle)	EOT ^a	30 days (±3 days) after last dose of study treatment and then every 3 months thereafter (±7 days) ^b
			Cycle 1 – EOT		
Survival status/subsequent therapy/ other malignancies				X	X ^k
Safety Assessments (See Section 8)					
Adverse events and concomitant therapy	X		X	X	X
Physical Examination height and weight	X		Day 1 of each cycle (height is measured at screening only)	X	
Vital signs ^l	X		Days 1, 3, and 17 of each cycle	X	
ECOG assessment	X		Day 1 of each cycle	X	

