4. STUDY DESIGN

4.1. Overall Design

This is an open-label study. The study will consist of 2 sequential parts, Part 1 and Part 2, as described below. The purpose of Part 1 is to select a dose schedule based on the totality of the data, including CR rate and other efficacy endpoints, PK, biomarkers, and safety. The purpose of Part 2 is to further evaluate and confirm the efficacy and safety of the combination therapy at the selected dose of cusatuzumab.

NOTE: Part 2 of the study will not be conducted because further development of this regimen (cusatuzumab in combination with azacitidine) in patients with unfit AML will not be pursued due to the evolving treatment landscape in AML.

NOTE: After 22 Oct 2021, ongoing subjects (on treatment or in follow-up) will be treated and assessed according to a reduced schedule of assessment (Table 1A).

Part 1 of the study is a randomized study of 2 doses of cusatuzumab in combination with azacitidine in patients with previously untreated AML who are not eligible for intensive chemotherapy. Part 2 of the study is an expansion of the selected dose. The study will include a Screening Phase, a Treatment Phase, and a Follow-up Phase. The Screening Phase will be up to 28 days prior to randomization. The Treatment Phase will extend from Cycle 1/ Day 1 until study intervention discontinuation. Participants will be treated with their assigned dosing regimen until disease progression, relapse, unacceptable toxicity, or withdrawal due to investigator discretion or withdrawal of consent. The Follow-up Phase will begin once a participant discontinues study intervention, and will continue until death, loss to follow up, consent withdrawal for study participation, or study end, whichever occurs first. Safety and efficacy data will be closely monitored on an ongoing basis by the Sponsor's central clinical team.

Part 1:

During Part 1, participants will be stratified by type of AML (de novo versus secondary AML) and ECOG score (0-1 versus 2) and then assigned randomly in a 1:1 ratio to receive cusatuzumab and azacitidine according to 1 of the following 2 dosing regimen groups:

- Group A: Azacitidine 75 mg/m² SC or IV on Day 1 through Day 7, cusatuzumab 10 mg/kg IV on Day 3 and Day 17 of each 28-day cycle
- Group B: Azacitidine 75 mg/m² SC or IV on Day 1 through Day 7, cusatuzumab 20 mg/kg IV on Day 3 and Day 17 of each 28-day cycle

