8.3. Adverse Events and Serious Adverse Events

Timely, accurate, and complete reporting and analysis of safety information from clinical studies are crucial for the protection of participants, investigators, and the Sponsor, and are mandated by regulatory agencies worldwide. The Sponsor has established Standard Operating Procedures in conformity with regulatory requirements worldwide to ensure appropriate reporting of safety information; all clinical studies conducted by the Sponsor or its affiliates will be conducted in accordance with those procedures. Adverse events will be reported by the participant (or, when appropriate, by a caregiver, surrogate, or the participant's legally acceptable representative).

For further details on adverse events and serious adverse events (Definitions and Classifications; Attribution Definitions; Severity Criteria; Special Reporting Situations; Procedures) as well as product quality complaints, refer to Appendix 4 Section 10.4, Adverse Events: Definitions and Procedures for Recording, Evaluating, Follow-Up, and Reporting.

8.3.1. Time Period and Frequency for Collecting Adverse Event and Serious Adverse Event Information

All Adverse Events

All adverse events and special reporting situations, whether serious or non-serious, will be reported from the time a signed and dated ICF is obtained until 30 days after the last dose of study intervention or until the start of subsequent anti-AML therapy, if earlier. Serious adverse events, including those spontaneously reported to the investigator within 30 days after the last dose of study intervention, must be reported using the Serious Adverse Event Form. The Sponsor will evaluate any safety information that is spontaneously reported by an investigator beyond the time frame specified in the protocol.

Serious Adverse Events

All serious adverse events occurring during the study must be reported to the appropriate Sponsor contact person by study-site personnel within 24 hours of their knowledge of the event.

Information regarding serious adverse events will be transmitted to the Sponsor using the Serious Adverse Event Form, which must be completed and signed by a physician from the study site and transmitted to the Sponsor within 24 hours. The initial and follow-up reports of a serious adverse event should be made by facsimile (fax).

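### The AE tables take every event reported since consent because the intervention-emergent definition is applied to none of them, so pre-dose events enter the dose-group percentages

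*SAP*

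**What the plan says.** **Collection.** Protocol 8.3.1 says that adverse events "will be reported from the time a signed and dated ICF is obtained until 30 days after the last dose of study intervention". Reporting stops sooner if subsequent anti-AML therapy begins first.

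**Definition.** The definition in SAP 5.1 has two limbs. The first reads: "Intervention-emergent adverse events are adverse events with onset during the intervention phase". The second limb brings in a further kind of event: "or that are a consequence of a pre-existing condition that has worsened since baseline". Neither document says when the intervention phase starts or ends.

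**Analysis rule.** The next sentence of SAP 5.1 is "All reported adverse events will be included in the analysis". Protocol 9.4.2 has the same definition and the same sentence. Six summaries follow: all events, Grade 3 or higher, serious, leading to treatment discontinuation, leading to death, and special interest. None is limited to emergent events. Each event is reported as the percentage of participants with at least one occurrence, by group.

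**Population.** The safety set in SAP 2.1 requires at least one dose of study drug. It sets no limit on event onset.

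**Phases.** Protocol 4.1 says: "The Screening Phase will be up to 28 days prior to randomization". It also says "The Treatment Phase will extend from Cycle 1/ Day 1 until study intervention discontinuation", and "The Follow-up Phase will begin once a participant discontinues study intervention". Table 1 of the Protocol places randomization as follows: "Within 72 hours of first dose".

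**The concern.** A definition of emergent events normally serves to limit the main AE tables to what happened on treatment. Here it is written and then bypassed. A treated participant whose only occurrence of a term began during screening counts as having that event in the 10 mg/kg or 20 mg/kg column.

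This population can have such events. Inclusion criterion 4.1 allows leukapheresis, hydroxyurea and one dose of cytarabine during screening, and nothing stops events that follow them from being tabulated under a cusatuzumab dose group. With Part 2 cancelled and Part 1 reported descriptively (SAP 1.6), these percentages are a main safety result of the study.

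A second weakness shows if someone tries to repair the tables by simply applying the definition as it stands. Because the intervention phase has no stated end, new events shortly after the last dose could be dropped, although Protocol 8.3.1 collects them.

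**Working it through.** The plan states no figure to reproduce. The check compares the passages and adds up window lengths.

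**1. Do pre-dose events reach the tables?** An event is tabulated if it was reported (Protocol 8.3.1, from consent), if the participant is in the safety set (SAP 2.1, at least one dose), and if no onset rule removes it. SAP 5.1 has no onset rule for any listed summary. So pre-dose events in treated participants are counted, while events in participants who were never dosed are not.

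**2. How long is the pre-dose window?** Screening is up to 28 days (Protocol 4.1), and randomization falls within 72 hours, or 3 days, of first dose (Protocol Table 1). 28 + 3 = 31 days. This is a maximum: it assumes consent at the start of a full screening period and the full 72 hours.

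**3. What share of reporting time is that?** Assume the maximum window, a last dose on Day 17 of the final 28-day cycle, and 30 further days of reporting.

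| Cycles | Pre-dose + on treatment + post-dose (days) | Pre-dose share | Post-dose share |
|---|---|---|---|
| 1 | 31 + 17 + 30 = 78 | 31/78 = 40% | 30/78 = 38% |
| 3 | 31 + 73 + 30 = 134 | 31/134 = 23% | 30/134 = 22% |
| 8 | 31 + 213 + 30 = 274 | 31/274 = 11% | 30/274 = 11% |

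These are shares of time, not of events.

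**4. What is the effect on a percentage?** For any term, the overstatement equals the proportion of treated participants whose only occurrence began before first dose. The documents give no such proportion. For a dose contrast, let p0 be the pre-dose probability of the term, the same in both groups, and let pA and pB be the on-treatment probabilities, independent of pre-dose occurrence. The tabulated probability is 1 − (1 − p0)(1 − p), so the tabulated difference is (1 − p0)(pA − pB). The contrast shrinks by the fraction p0. Purely as an illustration, p0 of 5% to 20% would shrink it by 5% to 20%; nothing in the documents supports any particular value.

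**5. Which tables are affected?** The special-interest event is a Grade 3 or higher infusion-related reaction (Protocol 8.3.5), which cannot precede dosing, so that table is unaffected. The other five have no onset limit.

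**6. What if the emergent definition were applied?** The nearest defined term is the Treatment Phase, which ends at discontinuation. If that is what is meant, new-onset events in the following 30 days are not emergent. The worsening limb has no end date, so a pre-existing condition that worsens in that period can still qualify. With the half-lives in Protocol 2.2.2.1 (8.3 to 13.1 days across the two studies reported), 30 days is 30/13.1 = 2.3 to 30/8.3 = 3.6 half-lives, so early post-dose events occur under exposure.

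**7. Baseline.** SAP 2.3 and 2.4 tie baseline to randomization, not first dose. If the worsening limb uses that baseline, it can capture worsening in the up to 72 hours before dosing.

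**The case against.** The strongest case on the other side is that including everything is conservative and hides no toxicity. Pre-dose events should balance across randomized groups on average, and SAP 1.6 limits Part 1 to descriptive summaries. Other rules also narrow what counts before dosing. An adverse event must be new or aggravated relative to the baseline condition, and expected disease progression is generally not one (Protocol Appendix 4). Active systemic infection is an exclusion, and a participant who ceases to be eligible before first dose should not enter (Protocol 5.2).

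These points stand, and they limit the size of the problem. They do not remove it: balance across groups leaves each group's incidence too high, and the contrast is diluted.

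Three stronger readings are tempting, and the documents support none of them.
- A reader might infer that emergent status ends at discontinuation, so that late events are being lost now. That endpoint is only inferred from the Treatment Phase. No listed table is emergent-only, so events in the 30 days after last dose are kept. One table cannot both add pre-dose events under the all-reported rule and lose late events under the emergent rule.
- A reader might infer that pre-dose events are being attributed to study drug. The tables are all-cause, and investigators record relatedness separately (Protocol Appendix 4).
- A reader might put a figure in percentage points on the inflation. The documents contain nothing to anchor one.

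**Conclusion.** The point holds as a defect in a stated rule. Following SAP 5.1 as written puts pre-dose events of treated participants into the all-cause AE percentages by dose group and overstates on-treatment incidence. The window is at most 31 days per participant, on the assumption of consent at the start of screening. The size of the overstatement cannot be estimated from the documents.

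The post-dose issue is a latent ambiguity, not a current loss. It would matter only if the emergent definition were applied without first defining the intervention phase, and then only for new-onset events.

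**What to change.** In SAP 5.1:
- Define treatment-emergent as onset, or worsening relative to the status before first dose, from the first dose of any study drug to the end of the Protocol 8.3.1 window (30 days after last dose, or start of subsequent anti-AML therapy if earlier).
- State that the main AE tables use this definition.
- Put pre-dose events in a separate listing.
- Replace the sentence that brings all reported events into the analysis.

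Record the change from Protocol 9.4.2 in SAP 1.6, since the same sentence stands there.

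The cost is slight extra programming and a documented departure from the protocol wording. No new data are needed, because the window is the one already used for collection.

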6.6. Dose Modification

Participants will be treated with their assigned dosing regimen until disease progression, relapse, unacceptable toxicity, or withdrawal due to investigator discretion or withdrawal of consent.

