If the number of participants at each stage is not exactly as specified in [Table 1](#), the Pocock beta-spending function with an overall beta level of 10% will be adjusted based on the actual number participants.

The above statistical criteria for Part 1 will be served as guidance; the totality of the data including other efficacy outcomes (eg, duration of CR), available safety, and PK/PD data will be considered in making a decision at each stage. If both dose schedules warrant proceeding into Part 2 per the above statistical criteria, only one dose schedule will be extended into Part 2 based on the observed CR rate as well as available data of other efficacy, safety, and PK/PD.

Table 1: Statistical Decision Parameters for Study Part 1: Observed CR, 1-Sided Confidence Interval (CI), and Statistical Decision

	Number (%) of Observed CR	1-Sided CI Upper Bound ¹ (%)	Decision	False Negative Error ²	False Positive Error ³
Stage 1, n=15	1 (6.7)	26.7	Stop	≤4%	NA
	2 (13.3)	34.9			
	3 (20.0)	42.3	Continue to Stage 2	NA	≤50%
	4 (26.7)	49.3			
Stage 2, n=30	5 (16.7)	30.5	Stop	≤5%	NA
	6 (20.0)	34.3			
	7 (23.3)	37.9	Continue to Stage 3	NA	≤32%
	8 (26.7)	41.5			
Stage 3, n=50	11 (22.0)	32.3	Stop	≤6%	NA
	12 (24.0)	34.4			
	13 (26.0)	36.6	Continue to Part 2	NA	≤14%
	14 (28.0)	38.7			

¹ 96%, 95%, and 94% for Stage 1, 2, and 3, respectively.

² False negative error: probability of a “stop” decision, when the true CR rate is ≥35%.

³ False positive error: probability of a “continue” decision, when the true CR rate is ≤20%.

Note: All statistical inferences are based on Wilson Score statistics without continuity correction.

Study Part 2

For Part 2, 1 interim analysis of CR rate is planned to include 80 participants. The null hypothesis of a CR rate of 20% will be rejected if the 1-sided nominal p-value is ≤0.01221. If the null hypothesis is not rejected at this interim analysis, the final analysis will be performed with 100 participants, and the null hypothesis will be rejected if the 1-sided nominal p-value is ≤0.02144. The O’Brien-Fleming alpha-spending, and Wilson Score test without continuity correction is to be implemented for the interim and final analyses.

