1.6. Changes of Study Conduct and Planned Analyses

The study did not proceed into Part 2 per decision by study Sponsor and the DRC upon completion of the analyses in all 3 stages in study Part 1. Data from study Part 1 will be summarized with descriptive statistics without formal comparison or hypothesis testing.

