3.5. Extent of Exposure

The following will be summarized by treatment group, and within each treatment group, by azacitidine and cusatuzumab: total dose prescribed, total dose administered, dose intensity (mg/m²/cycle azacitidine and mg/kg/cycle for cusatuzumab), and relative dose intensity (actual dose intensity divided by prescribed dose intensity).

Total treatment duration in months, total number of cycles, and cycle delay will be summarized by treatment group.

Number and percent of participants who switched the cusatuzumab dose level will also be provided.

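### Adverse event incidence by dose is planned only as a crude percentage over open-ended, outcome-dependent time at risk, so unequal treatment duration alone can separate the two doses

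*SAP*

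**What the plan says.** - **AE measure.** SAP 5.1 states that for each event "the percentage of participants who experience at least 1 occurrence of the given event will be summarized by intervention group". Protocol 9.4.2 uses the same sentence. SAP 5.1 continues: "In addition, comparisons between intervention groups will be provided if appropriate". No method is given for those comparisons.
- **Treatment length.** Protocol 6.6: "Participants will be treated with their assigned dosing regimen until disease progression, relapse, unacceptable toxicity, or withdrawal due to investigator discretion". Withdrawal of consent also ends treatment. There is no fixed number of cycles.
- **AE collection.** Protocol 8.3.1 collects AEs from consent "until 30 days after the last dose of study intervention or until the start of subsequent anti-AML therapy, if earlier".
- **Exposure.** SAP 3.5: "Total treatment duration in months, total number of cycles, and cycle delay will be summarized by treatment group". This is a separate table, and nothing connects it to the AE tables.
- **Use of the data.** Protocol section 3 lists the safety profile as a secondary endpoint. SAP 1.5 says that for Part 1 decisions "the totality of the data including other efficacy outcomes (eg, duration of CR), available safety, and PK/PD data will be considered". SAP 1.6 then records that the study did not go on to Part 2, and adds: "Data from study Part 1 will be summarized with descriptive statistics without formal comparison or hypothesis testing".

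Neither document plans a person-time rate, a time-to-first-event estimate or an AE table limited to a common period.

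**The concern.** The percentage with at least one event depends on two things: how often events occur and how long participants are watched. Here the second is itself an outcome. A participant who responds and stays on treatment is observed for longer than one who progresses early, and so has more opportunity for a first event. A dose that holds participants on treatment longer can therefore show higher percentages at the same event rate. A dose with many early stops can look safer than it is. The worst-grade shift tables in SAP 5.1 and 5.2 accumulate over the same unequal time.

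At stake is how the by-dose safety profile will be read when Part 1 is reported. A descriptive table with two dose columns will be read across, and SAP 5.1 leaves room for doing so.

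**Working it through.** The documents state no AE rate or treatment duration by dose for this study, so there is no plan figure to reproduce. The calculation shows how large the effect could be under stated assumptions.

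**Inputs**
- AE window: time on treatment plus 30 days, taken as 1 month (protocol 8.3.1). Earlier anti-AML therapy would shorten it.
- Group size: up to 50 per dose (SAP 1.4).
- Assumed: a constant first-event hazard h, the same in both doses, of 0.1 or 0.2 per month.
- Assumed: exponential time on treatment with mean m months, independent of the event.

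**Formula.** Crude percentage = 1 − exp(−h) × (1/m) / (1/m + h). The factor exp(−h) is the chance of no event in the 1-month tail.

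**Worked case, h = 0.1**
- m = 4: 1 − 0.9048 × 0.25/0.35 = 35.4%
- m = 6: 1 − 0.9048 × 0.1667/0.2667 = 43.4%
- Difference: 8.1 points before rounding, about 4 participants of 50.

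| Mean months | h = 0.1 | h = 0.2 |
|---|---|---|
| 4 v 6 | 35.4% v 43.4% (8.1 points) | 54.5% v 62.8% (8.3 points) |
| 3 v 6 | 30.4% v 43.4% (13.1 points) | 48.8% v 62.8% (14.0 points) |

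Over a wider grid (h from 0.02 to 0.20; 4 v 6, 4 v 8 and 6 v 9 months) the difference runs from 3.2 to 14.4 points. Leaving out the tail, with crude percentage = h/(h + 1/m), gives 9 to 10 points for 4 v 6 and 14 to 17 for 3 v 6. That overstates the effect, because the protocol does collect AEs in the tail.

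**What the alternatives give on the same inputs**
- *Person-month rate.* With a constant hazard, expected time at risk to first event or end of observation is the crude percentage divided by h. For h = 0.1 that is 3.54 months (m = 4) and 4.34 months (m = 6). The rates are 0.354/3.54 = 0.1 and 0.434/4.34 = 0.1, so the artefact is gone.
- *Cumulative incidence at 84 days, censoring at end of AE observation.* 84/30.4375 = 2.76 months (SAP 2.3 conversion). The estimate is 1 − exp(−0.1 × 2.76) = 24.1% in both doses, and 42.4% in both for h = 0.2.

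**Where the picture changes: front-loaded events.** Suppose 25% have an event, all in month 1, with mean durations of 4 v 8 months.
- Crude percentage: about 22% v 24% if risk stops at discontinuation, and 25% in both if the 30-day tail keeps month 1 fully observed. The artefact is small or absent.
- Person-month rate, counting 1 month for each participant with an event and m + 1 months for the rest: 0.25/(0.75 × 5 + 0.25 × 1) = 0.0625 v 0.25/(0.75 × 9 + 0.25 × 1) = 0.0357. The rate now falls only because exposure is longer, which is the opposite bias.

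**The case against.** The case on the other side has five parts.

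- **No dose is being chosen for Part 2.** A reader might infer from SAP 1.5 that biased safety percentages would steer the Part 2 dose. The documents do not support that for these tables. SAP 1.6 and the protocol notes say Part 2 is not conducted, and Part 1 is summarised descriptively. This stands, and it limits the consequence to interpretation.
- **No duration difference is documented.** A reader might infer that 20 mg/kg will look more toxic. Protocol 2.1.4 does report that neither 20 mg/kg complete responder had progressed after at least 60 weeks, while all 10 mg/kg subjects later progressed. That is three subjects per dose, and protocol 4.2.1 describes similar safety and efficacy at the two doses. The direction is open.
- **Exposure is tabulated.** SAP 3.5 would make an imbalance visible. It would not tell a reader how far the percentages have moved because of it.
- **The size is modest against noise.** For 35.4% v 43.4% with 50 per group, the standard error of the difference is √[(0.354 × 0.646 + 0.434 × 0.566)/50] = 9.7 points. The 4 v 6 month artefact is below one standard error. This stands, but the artefact is systematic and would not average out with more participants.
- **Person-time can mislead too.** This also stands. The AE of special interest is Grade 3 or higher infusion-related reaction (protocol 8.3.5), and the protocol treats that risk as mainly early: it allows steroid premedication to be dropped after three reaction-free infusions (6.1.1) and post-infusion monitoring to stop after 3 reaction-free cycles (6.6.1). A person-month rate is the wrong measure for it.

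**Conclusion.** The point holds as a gap in how by-dose AE incidence is summarised. The planned percentage mixes event rate with time at risk, and time at risk depends on outcome. Under identical hazards of 0.1 to 0.2 per month, the resulting difference is about 8 points for mean durations of 4 v 6 months and 13 to 14 points for 3 v 6.

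These sizes rest on assumed hazards and durations, a constant hazard, and treatment duration independent of the event. If the doses have similar time on treatment, there is no artefact. For early events it is small.

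The point is a worthwhile, low-cost improvement to the reporting of a secondary endpoint. It is not an error in the trial's design. Nor should 3 cycles be read as the Data Review Committee's safety window: protocol 4.1 has the committee review cumulative data once participants have been treated for 3 cycles, which is a minimum follow-up.

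**What to change.** In SAP 5.1, keep the planned percentages and add, by dose:

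1. **For Grade 3 or higher AEs, serious AEs and AEs leading to discontinuation:** participants with a first event per person-month at risk. Time at risk ends at the first event, at last dose + 30 days, or at the start of subsequent anti-AML therapy, whichever comes first. State how a cusatuzumab dose switch is handled: either attribute later events and person-time to the dose being received, or censor at the switch. SAP 5 presents safety by actual treatment and does not settle this.
2. **For the same categories and the AE of special interest:** cumulative incidence of first event at a fixed time from first dose, for example 84 days (about 3 cycles). Handle the end of AE observation before that time explicitly, by censoring or, where it ends in death, as a competing event. Do not report a crude 84-day percentage, which counts early stops as event-free. Counting every early stop as a competing event would largely return that same percentage.

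Do not use the person-month rate for the AE of special interest. Read any between-dose safety statement alongside these measures.

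The cost is one extra table set from AE and dosing dates already collected. Measure (1) assumes a roughly constant hazard, and censoring in (2) assumes that stopping is unrelated to AE risk. That is why the two are paired and the percentages are kept.
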